9.3.2 Exclusion Criteria

Subjects are excluded from the study if any of the following criteria are met at screening or at day -1:

1. Prior receipt of a MERS vaccine or MVA immunizations.
2. Receipt of any vaccine in the 2 weeks prior to 1st trial vaccination (4 weeks for live vaccines) or planned receipt of any vaccine in the 3 weeks following the 2nd trial vaccination.
3. Known allergy to the components of the MVA-MERS-S vaccine product as eggs, chicken proteins, and gentamycin or history of life-threatening reactions to vaccine containing the same substances.
4. Known history of anaphylaxis to vaccination or any allergy likely to be exacerbated by any component of the trial vaccine.
5. Participation in a clinical trial or use of an investigational product within 30 days or five times the half-life of the investigational drug -whichever is longer- prior to receiving the first dose within this study.
6. Evidence in the subject's medical history or in the medical examination that might influence either the safety of the subject or the absorption, distribution, metabolism or excretion of the investigational product under investigation.
7. Clinically relevant findings in ECG, in particular prolonged QTc (B) of > 450 msec in males and > 460 msec in females.
8. Any positive result for HIV1/2, HCV antibody or HBs antigen testing.
9. Any confirmed or suspected immunosuppressive or immunodeficient condition, cytotoxic therapy in the previous 5 years, and/or diabetes.
10. Subjects with inflammatory, infectious and neuroinflammatory underlying disease which could cause an expected impairment of the blood brain barrier such as meningitis, multiple sclerosis, epilepsy, or Alzheimer's disease.
11. Any chronic or active neurologic disorder, including seizures, and epilepsy, excluding a single febrile seizure as a child.
12. Known history of Guillain-Barré Syndrome.
13. Active malignancy or history of metastatic or hematologic malignancy.
14. Suspected or known alcohol and/or illicit drug abuse within the past 5 years.
15. Moderate or severe illness and/or fever >38°C within 1 week prior to vaccination.
16. Administration of immunoglobulins and/or any blood products within the 120 days preceding study entry or planned administration during the study period. Oral or parenteral immunosuppressant and immunomodulating agents (including interferons) should be discontinued at least 4 weeks prior to first injection.
17. History of blood donation within 60 days of enrollment or plans to donate within the treatment phase (until the 2nd vaccination).
18. Receipt of chronic (defined as more than 14 days) immune suppressants or other immune-modifying drugs within 6 months of study inclusion (screening).
 - For corticosteroids, this will mean prednisone, or equivalent, greater than or equal to 0.5 mg/kg/day.
 - Intranasal and inhaled steroids are allowed. Topical steroids are permitted provided they are not required to be applied to injection site.
19. Subjects with skin lesions close to the injection site or active oral lesions will be excluded.
20. Thrombocytopenia, contraindicating intramuscular vaccination based on investigator's judgment.
21. Subjects with a significant infection or known inflammation.
22. History of relevant cardiovascular disorders or evidence of hyper- (sitting blood pressure systolic >140 or diastolic >90 mmHg) or hypotension (sitting blood pressure systolic <90 or diastolic <40 mmHg) at screening.
23. Subjects who are known or suspected not to comply with the study directives.

24. Any other significant finding that in the opinion of the investigator would increase the risk of the individual having an adverse outcome from participating in this study.

Additional criteria for the subjects receiving the 3rd vaccination:

Receipt of any vaccine in the 2 weeks prior to (4 weeks for live vaccines) or 3 weeks following the 3rd vaccination.

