9.4 Treatments

9.4.1 Treatments Administered

All eligible subjects will be allocated to one of the two dose cohorts according to the assignment list. Each subject will receive two or three vaccine injections administered as i.m. injections in the deltoid region of the upper arm muscle.

For safety reasons dose administration in each dose level will be performed in four groups. Dose administration for the first subject at all dose levels will be vaccinated 48 hours prior to the second groups (second and third subject) of this dose level. The second and the third subject will be vaccinated in an interval of at least 5 min and after a period of at least 48 hours after the first subject to assess for immediate hypersensitivity reaction (within 60 min after the vaccination) or cytokine release (within 24 hours following the vaccination). The next group of four subjects can be vaccinated in parallel (in intervals of at least 5 min) at least 24 hours after the second group and at least 24 hours before the last group. The last group of the dose cohort including five subjects will be dosed on the same day in intervals of at least 5 min. Dosing events are supervised by an Investigator.

Figure 1: Dose administration groups

A Local Safety Board will be established for this study. Planned 2nd immunization and dose escalation will occur following a review of the interim safety report. Interim safety reports will contain safety data obtained until day 7.

The second immunization for each subject will be done after the Local Safety Board reviewed individual safety data of the respective subject.

All subjects who consented to the study extension will be immunized a third time with a vaccine dose of 1×10^8 pfu MVA-MERS-S at 12 months (± 4 months) after the first vaccination.

For the decision about dose escalation safety data obtained until day 7 after the second immunization of all subjects of the first cohort will be taken into account.

A dose level may be repeated and furthermore, additional dose step(s) may be added but not exceeding dose of 1×10^8 pfu MVA-MERS. The decision to repeat and/or to modify the dose level and/or to add additional dose steps will be taken by the Local Safety Board and the Ethics Committee and Competent Authority will be notified.

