9.4.8 Prior and Concomitant Therapy

As only healthy subjects will be enrolled, concomitant use of any medicinal product is forbidden prior to dosing as defined in section 9.3.2 *Exclusion Criteria* of this protocol. Prior to the dosing, subjects will be asked about this point.

Any use of drugs will be documented specifying the substance, dose, time and reason for use.

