9.4.10.3 Screening, Confinement and Ambulatory Visits

9.4.10.3.1 Confinement (Day -1 to Day 1 and Day 27 to Day 29)

The Subjects will be admitted to the study ward in the evening on Day -1 going through regular check-in procedures including an ID check, vital signs, an inclusion/exclusion check, an alcohol breath test and a urine drug, and pregnancy test. The Subjects will stay on the ward until the morning of Day 1 experiencing blood draws for immunogenicity analysis, documentation of occurrence of any injection site reaction, systemic events/reaction and adverse event questioning throughout the confinement period. Subjects will be dismissed at the earliest after the 24 h after vaccination and after subjects were trained on the use of the diary.

This schedule will be repeated in for the second vaccination on day 27 to day 29.

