9.7 Adverse Events

9.7.1 Definition of Adverse Events, Period of Observation, Recording of Adverse Events

An **Adverse Event (AE)** is any untoward medical occurrence in a clinical investigation subject administered an Investigational Medicinal Product (IMP) and that does not necessarily have a causal relationship with this treatment. An AE can therefore be any unfavorable and unintended sign (including an abnormal laboratory finding), symptom, disease or exacerbation of a pre-existing condition temporally associated with the use of a medicinal (test) product, whether or not considered related to the medicinal product (ICH Guidance E2A 1995).

All AEs, including those associated with the protocol, are collected from the time after first administration of IMP until the defined follow-up period and are to be recorded on the appropriate AE pages in the eCRF and in source documents. Where possible, a diagnosis rather than a list of symptoms should be recorded. If a diagnosis has not been made then each symptom should be listed individually.

A solicited AE is a predetermined event occurring within 14 days after application of IMP, which may reflect safety concerns related to the investigational product. The solicited AEs for this study include:

- Swelling, redness/ erythema, induration, hematoma or pain at site of injection
- Fever
- Chills
- Myalgia (described to the subject as generalized muscle aches)
- Arthralgia (described to the subject as generalized joint aches)
- Fatigue
- Headache
- Gastrointestinal symptoms (nausea, vomiting, abdominal pain, loose stool and/or diarrhea)
- Malaise

All AEs must be followed to closure (the subject's health has returned to his/her baseline status or all variables have returned to normal), an outcome is reached, stabilization (the investigator does not expect any further improvement or worsening of the event), or the event is otherwise explained regardless of whether the subject is still participating in the study. When appropriate, medical tests and examinations are performed so that resolution of event(s) can be documented.

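### Exclusion 2, as worded, bars no outside vaccine between doses 1 and 2 and sets no washout before dose 2, although dose 3 has one

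*Protocol*

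**What the plan says.** - **Exclusion 2 (Protocol 9.3.2, repeated in the synopsis).** It has two limits. The first is tied to dose 1: "Receipt of any vaccine in the 2 weeks prior to 1st trial vaccination (4 weeks for live vaccines"). The second is tied to dose 2: "planned receipt of any vaccine in the 3 weeks following the 2nd trial vaccination". The interval between the doses is not named.
- **Dose 3.** The added criterion for the boost has its own washout, "Receipt of any vaccine in the 2 weeks prior to (4 weeks for live vaccines"), and a 3-week bar afterwards.
- **Exclusion 17.** For blood donation the interval between doses is named: "plans to donate within the treatment phase (until the 2nd vaccination").
- **Section 9.4.8.** It says that "concomitant use of any medicinal product is forbidden prior to dosing as defined in section 9.3.2", which leads back to exclusion 2.
- **Rechecks before dose 2.** Sections 9.4.10.3.1 and 9.4.10.3.3 and Table 1a repeat the eligibility check on day 27. Section 9.4.1 adds: "The second immunization for each subject will be done after the Local Safety Board reviewed individual safety data of the respective subject".

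**The concern.** A site that follows exclusion 2 to the letter may let a subject receive a non-study vaccine at any time between the two doses, including shortly before dose 2. Vaccines commonly cause fever, myalgia, fatigue and headache, which are among the solicited systemic events here. They can also cause unsolicited events or shift laboratory values. All of these feed the primary endpoints in section 8.2, and there is no control arm against which to separate them.

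Causality assessment does not fully repair this. Section 9.7.1 defines solicited events by timing: "A solicited AE is a predetermined event occurring within 14 days after application of IMP". An event judged not related therefore stays in the count. The holding rules for solicited events in section 9.3.3.3 also carry no relatedness condition, whereas the rule for unsolicited events does.

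**Working it through.** The protocol states no figure to reproduce. The check is a reading of the text and a count of days.

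**Inputs**
- Dose 1 on day 0 and dose 2 on day 28 (synopsis, section 8.1).
- Exclusion 2: 14 days (28 if live) before dose 1; 21 days after dose 2.
- Dose-3 criterion: 14 days (28 if live) before, 21 days after.
- Confinement: evening of day -1 to morning of day 1, repeated for days 27 to 29 (section 9.4.10.3.1: "Subjects will be dismissed at the earliest after the 24 h after vaccination").
- Event windows: solicited 14 days, unsolicited 28 days after vaccination (section 8.2).
- Safety blood draws between doses (Table 1a): days 1, 3, 7, 14 and 27.

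**Days barred as worded**
- Before dose 1: days -14 to -1 (days -28 to -1 if live).
- After dose 2: days 29 to 49.
- Days 1 to 27 lie in neither window.

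**Practical opening, leaving out days spent wholly or partly on the ward**
- Full off-ward days are 2 to 26: 26 - 2 + 1 = 25.
- Solicited window, days 1 to 14: open on days 2 to 14, 13 of 14.
- Unsolicited window, days 1 to 28: open on days 2 to 26, 25 of 28.
- Safety blood draws that could follow an outside vaccine: days 3, 7, 14 and 27, which is 4 of 5.

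**Washout before dose 2, if the rule for doses 1 and 3 applied**
- Any vaccine: days 14 to 27, 14 days. Barred as worded: 0. Off the ward: days 14 to 26, 13 days.
- Live vaccines: days 0 to 27, 28 days. Barred as worded: 0. Off the ward: days 2 to 26, 25 days.

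**Weight of one subject:** 1/12 = 8.3 percentage points of a cohort.

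**Does another provision close the gap?**
- Section 9.4.8 has no time window of its own and refers to 9.3.2. It cannot be a blanket ban on medicines, since section 9.3.2.1 accepts oral contraceptives.
- The day-27 check re-reads a washout tied to dose 1. The lead-in to 9.3.2 itself names only screening and day -1.
- Exclusions 6, 15 and 24 concern medical findings, recent illness and investigator judgement. None is a vaccine rule.
- The individual safety review before dose 2 can reveal an outside vaccine but does not prohibit one.

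**The protocol's own dose-3 standard applied to doses 1 and 2.** Three weeks after dose 1 covers days 1 to 21, and two weeks before dose 2 covers days 14 to 27. These overlap, so the bar would run unbroken from day -14 (day -28 if live) to day 49.

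**The case against.** The strongest reply is that exclusion 2 describes one block. It limits the time before the first dose and after the second, the two outer ends of a short series. Read as two isolated windows it would protect dose 2 afterwards but not dose 1, for which no reason is visible. Dose 3 stands alone about a year later and was added by amendment, so it needs limits on both sides. That fits the one-block reading equally well. The comparison with exclusion 17 is also weak: inclusion 9 already bars blood donation throughout the study, so the contrast may only show uneven drafting.

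Detection is good. Concomitant medication is recorded from day 0, medical history is updated on day 27, each subject's data are reviewed before dose 2, and every event receives a causality judgement. No confirmatory test is planned. The day counts show when a vaccine could be given, not how many observations would be affected. One subject moves an incidence by 8.3 points only if otherwise free of that event. Solicited local events are tied to the injection site and would be largely unaffected.

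Most of this stands and limits the weight of the point. It does not remove it: the one-block reading is plausible but unwritten, and the safeguards make an outside vaccine visible without forbidding it.

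**Conclusion.** The concern holds as a minor point about wording. Followed literally, the criterion admits an outside vaccine inside the dose-1 safety windows, and dose 2 has less written protection than doses 1 and 3, with no reason given. The day counts assume dosing exactly on days 0 and 28, set aside partial ward days, and count event windows from the day after dosing. No effect on the endpoints is claimed, because the documents give no rate of outside vaccination. One affected subject could not alone trigger the solicited-event holding rules, which need more than 25% of injections and at least two individuals.

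**What to change.** Reword exclusion 2 and the matching synopsis line as one unbroken interval, for example: *any non-study vaccine received or planned at any time from 14 days (28 days if live) before dose 1 through 21 days after dose 2*. Ask about it explicitly at the day-27 eligibility check. Medically urgent vaccines would still be given and recorded as protocol deviations. For subjects already dosed, use the concomitant-medication record to flag any non-study vaccine between doses when adverse events are reported.

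The cost is one phrase in two places and one question at an existing visit, with no new data collection. The downside is about four more weeks of vaccine restriction (days 0 to 28) for healthy volunteers. If a continuous bar was always intended, the change only writes it down.

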9.3.2.1 Reproductive Potential

The study population includes female of child-bearing potential (FOCP). FOCP have to agree to comply with the applicable contraceptive requirements of the protocol as named below for the duration of the study or females who are permanently sterilized (at least 6 weeks post-sterilization).

Effective contraception is defined as a contraceptive method with failure rate of less than 1% per year when used consistently and correctly and when applicable, in accordance with the product label for example:

- Oral contraceptives, either combined or progesterone alone,
- injectable progesterone,
- implants of etonogestrel or levonorgestrel
- oestrogenic vaginal ring
- percutaneous contraceptive patches,
- intrauterine device or intrauterine system,
- male partner sterilization at least 6 months prior to the female subject's entry into the study, and a monogamous relationship
- male condom combined with a vaginal spermicide (foam, gel, film, cream or suppository).
- male condom combined with a female diaphragm, either with or without a vaginal spermicide (foam, gel, film, cream, or suppository)

Condoms are to be used with the mentioned acceptable contraceptives.

9.3.2.2 Restrictions

Subjects will be asked to fast for at least 8 hours prior to dose administration in the morning of day 0 and 28 until 2 hours after vaccination.

9.3.3 Removal of Subjects from Therapy or Assessment

The study in its entirety may be discontinued prematurely by the PI or sponsor at any time (see below), and/or individual subjects may terminate their participation prematurely, or have their participation be terminated by the Investigator.

9.3.3.1 Withdrawal of Subject from the Study

The following circumstances may lead to discontinuation of the study by an individual subject who will then be recorded as a drop-out include but are not limited to the following:

- Withdrawal for personal reasons
- Adverse events necessitating withdrawal from the study
- Sudden incidence of diseases
- Circumstances in which the health of the subject would be endangered upon continued participation in the study
- Subject non-compliance with study requirements
- An AE, which requires discontinuation of the study involvement or results in inability to continue to comply with study procedures
- Significant protocol violation
- Lost to follow up

- Other (must be specified)

The reason for withdrawal will be recorded in the eCRF. If withdrawal is due to an AE, appropriate follow-up visits or medical care will be arranged, with the agreement of the subject, until the AE has resolved, stabilized or a non-trial related causality has been assigned. The Local Safety Board may recommend withdrawal of subjects.

At least 3 documented attempts must be made within 2 weeks to contact any subject lost to follow-up at any time point prior to the last scheduled office visit. One of the documented attempts must include a written communication (e.g. post mail, courier) with acknowledgement of receipt requested (e.g. certified mail, registered mail) sent to the subject's last known address, requesting that they return any unused investigational medicinal product and return to the study site for final safety evaluations.

A replacing subject will be assigned to the same administration sequence as the drop-out and to an ID number which is the drop-out number plus 100 (drop-out subject number 102 means replacer number 202). In case of drop out after first administration of study medication a final examination should be performed whenever possible.

9.3.3.2 Handling Subjects with Premature Study Discontinuation

In the absence of a medical contraindication or significant protocol violation, every effort will be made by the Investigator to keep the subject in the study. If a subject has to be withdrawn, all efforts will be made to complete and report the trial observations as thoroughly as possible and to follow safety of the subject as per protocol.

Subjects who withdraw or are withdrawn from the study prior to injection will be replaced. No follow-up of these subjects will be performed and no data will be analyzed. Subjects withdrawing or withdrawn within the first 7 days after second injection will be replaced, and their data will be analyzed in the safety population (see section 9.8.1.2). Subjects withdrawing or withdrawn after study day 35 will not be replaced, and their data will be analyzed in the safety population and the per protocol population (see section 9.8.1.2).

When a subject withdraws from the study before the planned end of the study period, all investigations scheduled for the end-of-study visit should be performed if the subject agrees. End-of-study evaluation will be completed at the time of the subject's withdrawal, with an explanation of the reason for this entered onto the respective "end-of-study" section of the eCRF as follows:

- Adverse event (specify)
- Death
- Protocol violation (specify)
- Medical condition (specify)
- Consent withdrawal, not due to AE
- Lost-to follow-up
- Other (specify)

9.3.3.3 Criteria for Termination of the Study (Holding Rules)

Safety holding rules will apply throughout the entire study period. Further injections will be discussed with the Local Safety Board. Should a holding rule be activated, the PI will inform the sponsor. The sponsor has to inform the competent authorities and the ethics committee within 15 days.

If the event(s) occur in the higher-dose cohort, the follow-up phase of the lower dose cohort will continue. The discontinuation of a holding rule should be communicated to all entities in the same manner and timeframe as described above.

The Local Safety Board review will consider:

- The relationship of the AE or SAE to the vaccine
- The relationship of the AE or SAE to the vaccine dose, or other possible causes of the event
- If appropriate, additional screening or laboratory testing for other subjects to identify those who may develop similar symptoms, and alterations to the current informed consent form will be discussed

All injected subjects will be followed for safety until resolution or stabilization (if determined to be chronic sequelae) of their AE. AE grading will be done according to FDA's 2007 voluntary guidance: (14) or according to CTCAE v4 (15). Please refer to Table 3- Table 5 for further details.

The holding rules are as follow:

- Solicited (expected) local adverse events:
 - If more than 25% of injections (minimum 2 individuals) are followed by Grade 3 solicited swelling or pain or Grade 4 redness beginning within 3 days after injection (day of injection and one subsequent day) and persisting at Grade 3 (swelling or pain)/4 (redness) for >48 – 72 hours
- Solicited (expected) systemic adverse events:
 - If more than 25% of injections (minimum 2 individuals) are followed by Grade 3 solicited systemic AE (or Grade ≥ 3 physical observations as defined above and in Section 9.7.11) beginning within 3 days after study injection (day of injection and one subsequent day) and persisting at Grade ≥ 3 for >48 – 72 hours
- Unsolicited (unexpected) adverse events:
 - If more than 25% of subjects (minimum of 2 individuals) develop a Grade ≥ 3 unsolicited AE (including laboratory AE and physical observations) that is considered probably or definitely related to injection and persists at Grade 3 for >48 – 72 hours
- A serious adverse event occurs that may be related to the IMP

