9.5.2.8.9 Reactogenicity

To assess reactogenicity after each immunization body temperature and reaction are recorded for at least 14 days after vaccination or until any symptoms resolved if longer. According to the defined time frame of ± 2 days for the ambulatory visit on day 42 recording might be shortened to day 40. During confinement at the study ward temperature and solicited injection site and systemic reactions will be assessed and recorded by a designated member of the study team. After dismissal subjects are asked to maintain a diary to record daily temperature and solicited (expected) injection site and systemic reactions for 14 days after each dosing. Subjects will be asked to maintain a second diary for another 14 days to record medicinal events. As described above, the second diary after the second immunization should be maintained at least until day 40. Subjects will be trained on the thermometer and diary use.

The following items will be recorded:

- Daily temperature (incl. the method by which it was taken)
- Daily measurement of intensity grade of all other solicited (expected) injection site and systemic reactions
- Action taken for each recorded event (none, medication taken, physician consulted, hospitalization)

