9.10 Local Safety Board

During the trial, the Local Safety Board will review and judge the safety, tolerability, after each dose-step and prior to the next dose-step of the trial. Based on these data the Local Safety Board will/may decide

- Whether there will be a next dose cohort and if the planned dose for the next dose cohort has to be reduced.
- Whether there will be added additional dose step(s) or dose step(s) will be repeated.

Evaluation will take the results of the pre-clinical studies and the ongoing phase I studies in prior mentioned other countries into account.

An interim safety report, summarizing the safety (AEs, vital signs, 12-lead ECGs, and laboratory safety data) will be prepared and reviewed by the Principal Investigator and Medical Monitor before the second immunization for each dose cohort.

Planned dose escalation will occur after the second immunization of all subjects of the 1st dose group following a review of the interim safety report summarizing the safety (AEs, vital signs, 12-lead ECGs, and laboratory safety data) and any available immunological data by the Principal Investigator and Medical Monitor.

The dose for the next escalation step may be reduced if there are concerns about the safety. A dose level may be repeated and furthermore, additional dose step(s) may be added but not exceeding dose of 1×10^8 pfu MVA-MERS. The decision to repeat and/or to modify the dose level and/or to add additional dose steps will be taken by the Local Safety Board.

In addition, a Local Safety Board meeting will be conducted whenever safety relevant data occur that might have an influence on the trial.

Members of the Local Safety Board will be the medical monitor, as well as the Principal Investigator, or at least one of the deputies and a representative of the sponsor.

At a minimum the holding rules (criteria for termination of the study) specified in the protocol will automatically apply (if activated) for not proceeding with a higher dose.

The decisions of the Local Safety Board meeting will be briefly summarized by CTC North and signed by all members involved in the meeting and the decision. The summarized safety report of each Local Safety Board Meeting will be submitted to the competent national authority (Paul-Ehrlich-Institute) and the independent ethics committee (Ethik-Kommission der Ärztekammer Hamburg) for notification.

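### Both solicited holding rules define the onset window twice in one clause, as 3 days and as days 0-1, so a Grade 3 reaction starting on day 2 counts on one reading and not on the other

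*Protocol*

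**What the plan says.** Section 9.3.3.3 contains three percentage rules and one rule for a possibly related serious adverse event. The two solicited rules share one structure: more than 25% of injections (minimum 2 individuals) followed by a reaction of the named grade, with onset inside a window, persisting at that grade for >48-72 hours. The local rule names Grade 3 swelling or pain and Grade 4 redness. The systemic rule names Grade 3 systemic events, or physical observations of Grade 3 or above.

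The onset window in the local rule is "beginning within 3 days after injection (day of injection and one subsequent day"). In the systemic rule it is "beginning within 3 days after study injection (day of injection and one subsequent day").

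The third percentage rule has no onset window. It counts an "unsolicited AE (including laboratory AE and physical observations) that is considered probably or definitely related to injection". On scope, the section states: "Safety holding rules will apply throughout the entire study period".

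Section 9.7.1 fixes what is solicited: "A solicited AE is a predetermined event occurring within 14 days after application of IMP". Section 9.10 gives the rules their force. At a minimum, the holding rules "specified in the protocol will automatically apply (if activated) for not proceeding with a higher dose".

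**The concern.** A holding rule is useful only if two people applying it to the same data reach the same answer. Here the onset criterion is given in days and then explained in brackets by a different number of days. A reaction starting on day 2, and on the widest reading day 3, is inside the window or outside it depending on which half of the clause the reader follows.

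What is at stake is the automatic part of the safety control. These rules are the pre-specified minimum that blocks the higher dose without any discretion. If their activation can be argued either way, the decision falls back on the judgement of the Local Safety Board, which under section 9.10 consists of the medical monitor, the Principal Investigator or a deputy, and a sponsor representative. The statistical analysis plan is not the place to repair this, because the clause is operative stopping text in the protocol.

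**Working it through.** 1. Days covered by each reading, with day 0 as the day of injection:

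| Reading | Days | Calendar days |
|---|---|---|
| Bracket: injection day plus one | 0-1 | 2 |
| Three days, injection day counted as the first | 0-2 | 3 |
| Three days after the injection | 0-3 | 4 |

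The stated figure of 3 days is not reproduced by its own explanation, which gives 2. Day 2 is inside both three-day readings and outside the bracket. Day 3 is inside only the widest reading.

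2. Number of events that activates a solicited rule. This is the smallest whole number above 0.25 × n, and at least 2. The section does not say which injections form n, so I assume all injections given at the dose level up to that point.
- n = 12 (first injections of a cohort): 0.25 × 12 = 3, so 4 are needed (4/12 = 33%).
- n = 24 (both injections of a cohort): 0.25 × 24 = 6, so 7 are needed (7/24 = 29%).

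3. Same data, two results. All reactions below are Grade 3 pain that meets the persistence criterion.
- Four of 12 injections, all with onset on day 2. Three-day phrase: count 4, hold. Bracket: count 0, no hold.
- Three with onset on day 1 and one on day 2, of 12. Three-day phrase: count 4, hold. Bracket: count 3 = 25%, which is not more than 25%, no hold. A single disputed onset decides.

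4. Whether another rule picks up the disputed reactions. Listed reactions on days 2 and 3 are solicited under section 9.7.1, so the unsolicited rule does not take them. The exception is physical observations such as fever, which that rule names, and there a probable or definite relationship is required. The remaining rule needs a serious event. A non-serious Grade 3 local or subjective systemic reaction (pain or headache, for example) starting on day 2 therefore counts towards no rule if the bracket governs.

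5. Whether the wider window can be judged when decisions are taken. Section 9.4.1 bases escalation on "safety data obtained until day 7 after the second immunization of all subjects of the first cohort". An onset on day 3 followed for 72 hours reaches day 3 + 3 = day 6, inside that cut-off. The interim report before the second immunization also holds data to day 7.

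**The case against.** The strongest reply is that the consequence is small. The Local Safety Board reviews each subject's data before the second immunization, can meet whenever safety-relevant data arise, and under section 9.4.1 can decline to escalate for events that activate no holding rule. A possibly related serious event triggers a hold by itself. Section 7.3 reports only mild-to-moderate events with MVA vaccines, so more than 25% persistent Grade 3 reactions may be unlikely. All of this stands and limits the weight of the point. It does not make the clause readable, and it does not replace a rule that section 9.10 says applies automatically.

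A reader might go further and infer that the short window is itself an error, because Grade 3 local and subjective systemic reactions starting on days 4-14 remain solicited and enter no percentage rule on any reading. The reading of the text is right, but the documents do not show a mistake. A short window without a causality test, next to an unsolicited rule with a causality test and no window, is a coherent design. The statement that the rules apply throughout the study can mean that they are in force after every injection. Recording "for at least 14 days after vaccination or until any symptoms resolved if longer" serves the reactogenicity endpoints and does not oblige the holding rules to use the same period. A 14-day automatic trigger would also count intercurrent illness, and it could not be completed for the second dose at the day-7 escalation cut-off.

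**Conclusion.** The onset window in both solicited rules is wrong as written and should be corrected. The defect covers day 2 on either way of counting three days, and day 3 on the wider one. It can change the result of an automatic bar to escalation on identical data, with as little as one disputed onset among 12 injections. The counts of 4 of 12 and 7 of 24 rest on the assumption about the denominator stated above; the contradiction does not depend on it.

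I attach no probability to a changed decision. The protocol gives neither a rate of persistent Grade 3 reactions nor a distribution of onset days, and the local and systemic rules are counted separately, so any such figure would be assumption only. Nor does the finding show that escalation is unprotected: what is uncertain is the automatic stop, while Board review and the serious-event rule remain.

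As a remark and not an error: local and subjective systemic Grade 3 reactions with onset on days 4-14 are left to Board review and the serious-event rule. The sponsor may wish to confirm that this is intended.

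**What to change.** State one window in both solicited rules. The wider one is preferable in a first-in-human trial: keep the three-day phrase and replace the bracket by *(day of injection and the three subsequent days)*. Leave the grades, the threshold of more than 25% with a minimum of 2 individuals, the persistence criterion and the unsolicited rule as they are. If the sponsor meant days 0-1, the three-day phrase should go instead; either choice removes the contradiction.

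The change is a few words in two rules, made by amendment. It needs no new data, since temperature and solicited reactions are already recorded daily, and no delay, since a day-3 onset can be judged by day 7. The downside is a slightly higher chance of a hold, because day 2-3 onsets would now count without a causality judgement; the Board already weighs relationship to the vaccine when it reviews a hold. The change does not settle the persistence criterion, where the range of >48-72 hours leaves its own choice to the reader; the same amendment could name one limit.
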